**Appendix 4. ICD and MedDRA Codes For Select Safety Endpoints**

Event	ARTIS		BIOBADASER, BSRBR, RABBIT
	Operationalization	Validation ICD	Operationalization (Final list TBD based on reported endpoints).
Serious infections	Hospitalizations in the Patient Register listing as main diagnosis ICD10-codes below. If main diagnosis is RA, contributory diagnoses are also considered. A00-B99 (excluding A33 and A50), D73.3, E32.1, G00-G02, G04.2, G05-G07, H00.0, H44.0, H60.0-H60.3, H66-H67, H70, I30.1, I40.0, J00-J22, J32, J34.0, J36, J39.0-J39.1, J44.0, J85, J86, K04.4, K04.6, K04.7, K10.2, K11.3, K12.2, K14.0, K57.0, K57.2, K57.4, K57.8, K61, K63.0, K65.0, K65.1, K65.2, K65.9, L00-L08, L30.3, M00-M01, M46.2-M46.5, M60.0, M65.0, M71.0, M71.1, M72.6, M86, N13.6, N15.1, N15.9, N30.0 N30.8, N34.0, N41.2, N43.1, N45.2, N45.3, N45.4, N48.2, N61, N70, N73, N75.1	This algorithm has not been specifically validated in ARTIS, but the register itself is subject to strict quality assurance routines and has been validated several times. Refs: Ludvigsson et al. External Review and Validation of the Swedish National Inpatient Register, BMC Public Health, 2011 (11):450. http://www.socialstyrelsen.se/register/halsodataregister/patientregistret/inenglish .	Hospitalization and/or use of parenteral antibiotics+ MedDRA Infections and Infestations SOC 10021881.
HZ reactivation	Hospitalizations in the Patient Register listing as main diagnosis ICD10-codes B00 and B02. If main diagnosis is RA, contributory diagnoses are also considered.	The algorithm used to identify this endpoint in ARTIS has not been validated and is expected to only identify the most severe cases.	10019974 Herpes zoster, 10019983 Herpes zoster ophthalmic, 10030865 Ophthalmic herpes zoster, 10058428 Herpes zoster multi-dermatomal, 10063491 Herpes zoster oticus, 10065038 Herpes zoster disseminated, 10065119 Necrotising herpetic retinopathy, 10072210 Genital herpes zoster, 10074241 Varicella zoster gastritis, 10074245 Herpes zoster pharyngitis, 10074248 Herpes zoster meningoencephalitis, 10074253 Herpes zoster necrotising retinopathy, 10074254 Varicella zoster pneumonia, 10074254 Varicella zoster pneumonia, 10074259 Herpes zoster meningitis, 10074297 Herpes zoster cutaneous disseminated.

090177e199570500\Approved\Approved On: 13-Feb-2022 20:25 (GMT)

090177e199570500\Approved\Approved On: 13-Feb-2022 20:25 (GMT)

	ARTIS		BIOBADASER, BSRBR, RABBIT
Event	Operationalization	Validation ICD	Operationalization (Final list TBD based on reported endpoints).
CV risk	Major Acute Cardiovascular Events (MACE), combines MI, stroke, and fatal cardiovascular events: I00-I99 as main cause of death, or I20.0, I21, I60-I64 as diagnosis in in- or outpatient care.	
See Serious Infections
 
‘Outcome’ was defined as any first-ever ACS event, which in turn was defined as a primary discharge diagnosis of acute myocardial infarction or unstable angina pectoris, or as acute myocardial infarction being the underlying cause of death. For discharge diagnoses, the date of admission to hospital was considered the event date. This outcome definition has previously been validated in a Swedish early RA cohort, with a positive predictive value of 95%. In addition, a regional validation study of hospitalized acute MI and stroke found positive predictive values of 96% and 94% respectively, in the period 1977 to 1987.
 
Lindblad et al. Validity of register data on acute myocardial infarction and acute stroke. Scandinavian Journal of Public health 1993; 21 (1):3-9.
	
Fatal and non-fatal
 
10000891 Acute myocardial infarction; 10006147 Brain stem infarction; 10006148 Brain stem ischaemia; 10008034 Cerebellar infarction; 10008088 Cerebral artery embolism; 10008120 Cerebral ischaemia; 10008190 Cerebrovascular accident; 10014498 Embolic stroke; 10019005 Haemorrhagic cerebral infarction; 10019016 Haemorrhagic stroke; 10024033 Lateral medullary syndrome; 10028596 Myocardial infarction; 10028602 Myocardial necrosis; 10033697 Papillary muscle infarction; 10043647 Thrombotic stroke; 10049768 Silent myocardial infarction; 10051078 Lacunar infarction; 10055677 Haemorrhagic transformation stroke; 10056237 Migrainous infarction; 10059613 Stroke in evolution; 10060839 Embolic cerebral infarction; 10060840 Ischaemic cerebral infarction; 10061256 Ischaemic stroke; 10062573 Brain stem thrombosis; 10064961 Thalamic infarction; 10066591 Post procedural stroke; 10066592 Post procedural myocardial infarction; 10067167 Cerebellar embolism; 10067347 Thrombotic cerebral infarction; 10067462 Millard-Gubler syndrome; 10068621 Cerebellar ischaemia; 10068644 Brain stem stroke; 10069020 Basal ganglia infarction; 10070671 Cerebral septic infarct; 10070754 Inner ear infarction; 10071043 Basal ganglia stroke; 10071260 Carotid angioplasty; 10073945 Perinatal stroke; 10074422 Brain stem embolism;
 
Fatal only
 
10002886 Aortic aneurysm rupture; 10003173 Arterial rupture; 10003210 Arteriosclerosis; 10003212 Arteriosclerosis moenckeberg-type; 10006145 Brain stem haemorrhage; 10007522 Cardiac asthma; 10007554 Cardiac failure; 10007556 Cardiac failure acute; 10007558 Cardiac failure chronic; 10007559 Cardiac failure congestive; 10007559 Cardiac failure congestive; 10007560 Cardiac failure high output; 10007625 Cardiogenic shock; 10007684 Carotid arterial embolus; 10007686 Carotid artery aneurysm; 10007688 Carotid


090177e199570500\Approved\Approved On: 13-Feb-2022 20:25 (GMT)

	ARTIS		BIOBADASER, BSRBR, RABBIT
Event	Operationalization	Validation ICD	Operationalization (Final list TBD based on reported endpoints).
			artery thrombosis; 10008023 Cerebellar artery thrombosis; 10008030 Cerebellar haemorrhage; 10008076 Cerebral aneurysm ruptured syphilitic; 10008086 Cerebral arteriovenous malformation haemorrhagic; 10008089 Cerebral artery occlusion; 10008092 Cerebral artery thrombosis; 10008111 Cerebral haemorrhage; 10008118 Cerebral infarction; 10008132 Cerebral thrombosis; 10018985 Haemorrhage intracranial; 10022758 Intracranial aneurysm; 10022840 Intraventricular haemorrhage; 10022841 Intraventricular haemorrhage neonatal; 10024119 Left ventricular failure; 10024242 Leriche syndrome; 10034476 Pericardial haemorrhage; 10036511 Precerebral artery occlusion; 10039163 Right ventricular failure; 10039330 Ruptured cerebral aneurysm; 10042316 Subarachnoid haemorrhage; 10042434 Sudden death; 10047279 Ventricle rupture; 10048380 Aneurysm ruptured; 10048761 Atrial rupture; 10049418 Sudden cardiac death; 10049993 Cardiac death; 10050403 Carotid artery dissection; 10051093 Cardiopulmonary failure; 10051328 Carotid aneurysm rupture; 10052019 Femoral artery occlusion; 10053633 Cerebellar artery occlusion; 10053649 Vascular rupture; 10053949 Vascular pseudoaneurysm ruptured; 10055803 Haemorrhage coronary artery; 10058178 Aortic occlusion; 10060874 Aortic rupture; 10060953 Ventricular failure; 10060964 Arterial haemorrhage; 10062585 Peripheral arterial occlusive disease; 10062599 Arterial occlusive disease; 10063081 Acute left ventricular failure; 10063082 Acute right ventricular failure; 10063083 Chronic left ventricular failure; 10063084 Chronic right ventricular failure; 10064595 Haemorrhagic arteriovenous malformation; 10064601 Iliac artery occlusion; 10065441 Venous haemorrhage; 10065558 Aortic arteriosclerosis; 10067057 Basal ganglia haemorrhage; 10067116 Carotid arteriosclerosis; 10068119 Aortic dissection rupture; 10068119 Aortic dissection rupture; 10068230 Cardiorenal syndrome; 10069694 Brachiocephalic artery occlusion; 10069695 Subclavian artery occlusion;

090177e199570500\Approved\Approved On: 13-Feb-2022 20:25 (GMT)

		ARTIS		BIOBADASER, BSRBR, RABBIT	
Event	Operationalization	Validation ICD		Operationalization (Final list TBD based on reported endpoints).	
				10069696 Coeliac artery occlusion; 10071716 Vertebral artery dissection; 10072043 Central nervous system haemorrhage; 10072789 Iliac artery rupture; 10073565 Intracranial artery dissection; 10073565 Intracranial artery dissection; 10073681 Epidural haemorrhage; 10075449 Brachiocephalic arteriosclerosis; 10076203 Radiation associated cardiac failure.	
GI perforation	Hospitalizations in the Patient Register listing ICD10-codes: K22.3, K25.1, K25.2, K25.5, K25.6, K26.1, K26.2, K26.5, K26.6, K27.1, K27.2, K27.5, K27.6, K28.1, K28.2, K28.5, K28.6, K31.6, K35.0, K35.1, K57.0, K57.2, K57.4, K57.8, K63.0, K63.1, K63.2.	See Serious Infections ; Pharmacoepidemiol Drug Saf. 2011 Nov;20(11):1150-8. doi: 10.1002/pds.2215. Epub 2011 Aug 27. Validation of ICD-9-CM codes to identify gastrointestinal perforation events in administrative claims data among hospitalized rheumatoid arthritis patients.		10000099 Abdominal wall abscess; 10000285 Abscess intestinal; 10000582 Acquired tracheo-oesophageal fistula; 10002156 Anal fistula; 10002157 Anal fistula excision; 10002248 Anastomotic ulcer perforation; 10002924 Aorto-duodenal fistula; 10003012 Appendicitis perforated; 10009995 Colonic fistula; 10013536 Diverticular fistula; 10013538 Diverticulitis; 10013541 Diverticulitis intestinal haemorrhagic; 10013828 Duodenal fistula; 10013832 Duodenal perforation; 10013849 Duodenal ulcer perforation; 10013849 Duodenal ulcer perforation; 10013850 Duodenal ulcer perforation, nonobstructive; 10017815 Gastric perforation; 10017835 Gastric ulcer perforation; 10017836 Gastric ulcer perforation, obstructive; 10017866 Gastritis haemorrhagic; 10017877 Gastrointestinal fistula; 10017954 Gastrointestinal gangrene; 10017955 Gastrointestinal haemorrhage; 10018001 Gastrointestinal perforation; 10021305 Ileal perforation; 10021310 Ileal ulcer perforation; 10022647 Intestinal fistula; 10022694 Intestinal perforation; 10023174 Jejunal perforation; 10023178 Jejunal ulcer perforation; 10023804 Large intestine perforation; 10030181 Oesophageal perforation; 10034354 Peptic ulcer perforation; 10034358 Peptic ulcer perforation, obstructive; 10034397 Perforated peptic ulcer oversewing; 10034649 Peritoneal abscess; 10034674 Peritonitis; 10038073 Rectal perforation; 10038975 Retroperitoneal abscess; 10041103 Small intestinal perforation; 10046274 Upper gastrointestinal haemorrhage; 10048946 Anal abscess; 10048947 Rectal abscess; 10049583 Douglas' abscess; 10049764 Appendiceal abscess; 10050362 Anovulvar fistula;	

090177e199570500\Approved\Approved On: 13-Feb-2022 20:25 (GMT)

	ARTIS		BIOBADASER, BSRBR, RABBIT
Event	Operationalization	Validation ICD	Operationalization (Final list TBD based on reported endpoints).
			10050953 Lower gastrointestinal haemorrhage; 10051425 Enterocutaneous fistula; 10052211 Oesophageal rupture; 10052457 Perineal abscess; 10052488 Oesophageal ulcer perforation; 10052814 Perirectal abscess; 10052931 Colon fistula repair; 10052991 Intestinal fistula repair; 10053267 Rectal fistula repair; 10056086 Paraoesophageal abscess; 10056346 Anastomotic haemorrhage; 10056991 Enterocolonic fistula; 10056992 Oesophagobronchial fistula; 10058381 Oesophageal fistula repair; 10059175 Intestinal haemorrhage; 10060921 Abdominal abscess; 10061248 Intestinal ulcer perforation; 10061249 Intra- abdominal haemorrhage; 10061820 Diverticular perforation; 10061975 Gastrointestinal ulcer perforation; 10062065 Perforated ulcer; 10062070 Peritonitis bacterial; 10062570 Enterovesical fistula; 10065713 Gastric fistula; 10065879 Gastrointestinal anastomotic leak; 10066870 Aorto-oesophageal fistula; 10066892 Rectourethral fistula; 10067091 Gastropleural fistula; 10068792 Gastrosplenic fistula; 10071647 Infectious peritonitis.
PML	Hospitalizations in the Patient Register listing ICD10-codes: A81.2.	See Serious Infections .	TBD based on reported events.
NMSC	Identified through the Cancer register as all malignancies with ICD-O/2 code C44, and all basal cell cancers recoded in the register's subcomponent on basal cell cancers Alt: all invasive NMSC, identified as non-benign ICD-O/2 code C44, and no basal cell cancers.	About 99% of cancers have been morphologically verified. Reporting of incident cancers (including invasive malignancies as well as cancer in situ) is mandatory and semi automated, resulting in an estimated coverage greater than 95%.	10004146 Basal cell carcinoma; 10004178 Basosquamous carcinoma; 10004179 Basosquamous carcinoma of skin; 10006059 Bowen's disease; 10007390 Carcinoma in situ of skin; 10064055 Lip squamous cell carcinoma; 10063693 Malignant neoplasm of eyelid; 10040808 Skin cancer; 10055115 Skin cancer metastatic 10041834 Squamous cell carcinoma of skin.
Malignancy	All invasive malignancies recorded in the cancer register, excluding NMSC.	See NMSC .	Malignant or unspecified tumours (SMQ).
Lung Cancer	Identified through the Cancer Register. ICD-7: 162.1		HLTs: 10038723 Respiratory tract and pleural neoplasms malignant cell type unspecified NEC; 10024973 Lower respiratory tract neoplasms.

090177e199570500\Approved\Approved On: 13-Feb-2022 20:25 (GMT)

	ARTIS		BIOBADASER, BSRBR, RABBIT
Event	Operationalization	Validation ICD	Operationalization (Final list TBD based on reported endpoints).
			LLT: 10023292 Kaposi's sarcoma, lung;  Exclude PTs: 10043515 throat cancer; 10004280 benign lung neoplasm; 10061002 benign respiratory tract neoplasm, 10052247 bronchial neoplasm benign; 10014654 endobronchial lipoma; 10081106 sclerosing pneumocytoma.
Lymphoma	Identified through the Cancer Register. All non-Hodgkin Lymphoma: ICD-7: 200,202 All Hodgkin Lymphoma: ICD-7: 201 Chronic lymphocytic leukemia: ICD-7: 204.1	About 99% of cancers have been morphologically verified. Reporting of incident cancers (including invasive malignancies as well as cancer in situ) is mandatory and semi automated, resulting in an estimated coverage greater than 95%	Non-Hodgkin's lymphoma 10029547; Non-Hodgkin's lymphoma metastatic 10071535; Non-Hodgkin's lymphoma recurrent 10029600; Non-Hodgkin's lymphoma refractory 10029601; Non-Hodgkin's lymphoma stage I 10029602; Non-Hodgkin's lymphoma stage II 10029603; Non-Hodgkin's lymphoma stage III 10029604; Non-Hodgkin's lymphoma stage IV 10029605; Non-Hodgkin's lymphoma transformed recurrent 10061871; Non-Hodgkin's lymphoma unspecified histology aggressive 10063908; Non-Hodgkin's lymphoma unspecified histology aggressive recurrent 10029609; Non-Hodgkin's lymphoma unspecified histology aggressive refractory 10029610; Non-Hodgkin's lymphoma unspecified histology aggressive stage I 10029611; Non-Hodgkin's lymphoma unspecified histology aggressive stage II 10029612; Non-Hodgkin's lymphoma unspecified histology aggressive stage III 10029613; Non-Hodgkin's lymphoma unspecified histology aggressive stage IV 10029614; Non-Hodgkin's lymphoma unspecified histology indolent 10065856; Non-Hodgkin's lymphoma unspecified histology indolent stage I 10029622; Non- Hodgkin's lymphoma unspecified histology indolent stage II 10029623; Non-Hodgkin's lymphoma unspecified histology indolent stage III 10029624; Non-Hodgkin's lymphoma unspecified histology indolent stage IV 10029625;

090177e199570500\Approved\Approved On: 13-Feb-2022 20:25 (GMT)

	ARTIS		BIOBADASER, BSRBR, RABBIT
Event	Operationalization	Validation ICD	Operationalization (Final list TBD based on reported endpoints).
			Hodgkin's disease 10020206; Hodgkin's disease lymphocyte depletion stage I site unspecified 10020208; Hodgkin's disease lymphocyte depletion stage I subdiaphragm 10020209; Hodgkin's disease lymphocyte depletion stage I supradiaphragm 10020210; Hodgkin's disease lymphocyte depletion stage II site unspecified 10020211; Hodgkin's disease lymphocyte depletion stage II subdiaphragm 10020212; Hodgkin's disease lymphocyte depletion stage II supradiaphragm 10020213; Hodgkin's disease lymphocyte depletion type recurrent 10020215; Hodgkin's disease lymphocyte depletion type refractory 10020216; Hodgkin's disease lymphocyte depletion type stage III 10020217; Hodgkin's disease lymphocyte depletion type stage IV 10020218; Hodgkin's disease lymphocyte depletion type stage unspecified 10020219; Hodgkin's disease lymphocyte predominance stage I site unspec 10020220; Hodgkin's disease lymphocyte predominance stage I subdiaphragm 10020221; Hodgkin's disease lymphocyte predominance stage I supradiaphragm 10020222; Hodgkin's disease lymphocyte predominance stage II site unspec 10020223; Hodgkin's disease lymphocyte predominance stage II subdiaphragm 10020224; Hodgkin's disease lymphocyte predominance stage II supradiaphragm 10020225; Hodgkin's disease lymphocyte predominance type recurrent 10020227; Hodgkin's disease lymphocyte predominance type refractory 10020228; Hodgkin's disease lymphocyte predominance type stage III 10020229; Hodgkin's disease lymphocyte predominance type stage IV 10020230; Hodgkin's disease lymphocyte predominance type stage unspecified 10020231; Hodgkin's disease mixed cellularity recurrent 10020233; Hodgkin's disease mixed cellularity refractory 10020234; Hodgkin's disease mixed cellularity stage I site unspecified 10020235; Hodgkin's disease mixed cellularity stage I subdiaphragmatic 10020236; Hodgkin's disease mixed cellularity stage I supradiaphragmatic 10020237; Hodgkin's disease mixed cellularity stage II subdiaphragmatic 10020238; Hodgkin's disease mixed

090177e199570500\Approved\Approved On: 13-Feb-2022 20:25 (GMT)

	ARTIS		BIOBADASER, BSRBR, RABBIT
Event	Operationalization	Validation ICD	Operationalization (Final list TBD based on reported endpoints).
			cellularity stage II supradiaphragmatic 10020239; Hodgkin's disease mixed cellularity stage III 10020240; Hodgkin's disease mixed cellularity stage IV 10020241; Hodgkin's disease mixed cellularity stage unspecified 10020242; Hodgkin's disease nodular sclerosis 10020244; Hodgkin's disease nodular sclerosis recurrent 10020245; Hodgkin's disease nodular sclerosis refractory 10020246; Hodgkin's disease nodular sclerosis stage I 10073535; Hodgkin's disease nodular sclerosis stage II 10073534; Hodgkin's disease nodular sclerosis stage III 10020252; Hodgkin's disease nodular sclerosis stage IV 10020253; Hodgkin's disease recurrent 10020266; Hodgkin's disease refractory 10020267; Hodgkin's disease stage I 10020268; Hodgkin's disease stage II 10020269; Hodgkin's disease stage III 10020270; Hodgkin's disease stage IV 10061597; Hodgkin's disease unclassifiable 10020271; Chronic lymphocytic leukaemia 10008958; Chronic lymphocytic leukaemia (in remission) 10008959; Chronic lymphocytic leukaemia recurrent 10008961; Chronic lymphocytic leukaemia refractory 10008962; Chronic lymphocytic leukaemia stage 0 10008963; Chronic lymphocytic leukaemia stage 1 10008964; Chronic lymphocytic leukaemia stage 2 10008965; Chronic lymphocytic leukaemia stage 3 10008966; Chronic lymphocytic leukaemia stage 4 10008967; Chronic lymphocytic leukaemia transformation 10058717;
Fractures	Identified in patient register, in- or outpatient component.  Skull/face: S02 Neck: S12 Ribs/chest: S22 Lumbar spine/pelvis: S32 Shoulder/humerus: S42 Forearm: S52 Wrist/hand: S62 Femur: S72 Ankle/wrist: S82	The PPV for fractures in the Swedish NPR is extremely high: a validation of 647 patient charts the PPV of fracture in Swedish patient records was 1.00.  There is high accuracy for both a diagnosis of hip fracture and a fracture of any type in the Swedish Patient Register	HLTG   Bone and joint injuries (Primary Path) 
 
Exclude all PTs within HLT Bone and joint injuries NEC
 
Exclude the following individual PTs from other HLTs: Bone fissure, Cuboid syndrome, Fractured delayed union, Fracture infection, Fracture nonunion, Joint dislocation, Joint dislocation pathological, Metaphyseal corner fracture, Pathological fracture, Pseudoarthrosis, Pseudofracture, Anterior
 

Event	ARTIS		BIOBADASER, BSRBR, RABBIT
	Operationalization	Validation ICD	Operationalization (Final list TBD based on reported endpoints).
	Foot: S92 Fractures on multiple body parts: T02  Location of fracture not defined in detail: T08, T10, T12, T14.2.		labroligamentous periosteal sleeve avulsion lesion, Bankart lesion, Fracture of clavicle due to birth trauma, Radial head dislocation, Scapulothoracic disassociation, Dislocation of vertebra, Intervertebral disc injury, Spinal fusion fracture, Costal cartilage fracture, Costochondral separation, Dislocation of the sternum.  HLGT   Fractures (Primary Path) 
 
• Exclude all PTs within HLT Fracture complications
 
• Exclude the following individual PTs from other HLTs: Bone fissure, Metaphyseal corner fracture, Pathological fracture, Pseudofracture, Fracture of clavicle due to birth trauma, Scapulothoracic disassociation, Spinal fusion fracture, Costal cartilage fracture.
 

090177e199570500\Approved\Approved On: 13-Feb-2022 20:25 (GMT)

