### Objectives:

To estimate the rates of serious infections, malignancy (overall, excluding NMSC), lung cancer, subtypes of lymphoma, CV events MACE and MI, VTE (DVT and PE) and other safety events of interest, including fractures, among patients with RA in Sweden who initiate tofacitinib. Rates will also be estimated among 1) patients with RA who have not been treated with bDMARD or tsDMARD, 2) patients with RA who initiate bDMARDs, and 3) the general population to provide context for rates observed on tofacitinib. Pending feasibility, rates of malignancy (overall, excluding NMSC), lung cancer, subtypes of lymphoma, serious infection, CV events, MACE MI, VTE, and other event rates, including fractures, will be compared between tofacitinib-treated RA patients and other comparator cohorts using multivariable Cox regressions adjusting for sex, age, year of treatment start, treatment history, disease severity, comorbidities and other potential confounders for more refined evaluation of safety concerns. In response to the June 2021 signal evaluation procedure, subtypes of lymphoma, lung cancer, and MACE have been added as study endpoints (MI and lymphoma (overall) were already included as a study endpoints). Further, rates of events, including serious infections, MACE, MI, VTE, and malignancies excluding NMSC, will be estimated in elderly patients aged 65 years and older.

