## 9. RESEARCH METHODS

### 9.1. Study Design

This is an active surveillance study of existing nationwide cohorts in Sweden using linkages between drug-based registers, disease-based registers, national death register, cancer register, inpatient register, and outpatient register. All linkages are deterministic based on unique patient identifiers.

Rates of safety events of interest will be calculated in the four cohorts with 95% confidence intervals (CI) and reported as descriptive analyses. Data capture and follow-up methods are the same for all four cohorts within the Swedish Registers. This study will adhere to the ARTIS analytical protocol. No a priori hypotheses will be specified. Pending adequate sample size to permit adjustment for important variables for comparative analyses, 95% CI will be reported around hazard ratio (HR) estimates.

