### 9.2. Setting

Sweden is a Scandinavian country with 10 million inhabitants. The prevalence of RA in Sweden is around 0.7% and the overall incidence 41/100,000 per year.

Swedish health-care is tax-funded and offers universal access. Hospital referral is based on geography rather than insurance-status. Patients with RA are typically treated by rheumatologists, the vast majority of whom work in public and hospital-based clinics.

Health and demographic information is collected in a series of registers with a high degree of completeness resulting from the mandatory and semi-automated registration of their data. Based on each Swedish resident's unique personal identification number, issued to all Swedish residents alive in 1947 or born/immigrated thereafter, linkage of data from different registers is possible. The registers are maintained by governmental bodies (the main registers used in this project are held by the National Board of Health and Welfare (Socialstyrelsen) and Statistics Sweden), who may perform data linkages and provide de-identified data for research purposes.

Use of a RA treatment for a particular patient in Sweden has never been subject to a formal approval process (with the exception of a period during 2002-2003, when manufacturing issues led to reduced availability of etanercept), mandatory treatment history, or disease activity indices. Instead, the Swedish Society for Rheumatology has issued guidelines for the use of biologics, which are revised on an annual basis, but the ultimate decision to treat with biologics and which biologic to use have always resided with the treating rheumatologist.

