#### **9.2.1.4. General Population Cohort**

- Randomly selected from general population and region-, age- and gender-matched to RA patient cohorts, up to 5 population controls per tofacitinib exposed patient.

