Status at entry	Exposed Tofacitinib	Third biologic		Second biologic		Comparator Cohorts First biologic			
		TNFi	Non-TNFi	TNFi	Non-TNFi	TNFi	Non-TNFi	Biologics-naive	General population
Total days spent in hosp (median, IQR)									
Reason for discontinuing previous biologic									
Safety, of those with information (%)									
Inefficacy, of those with information (%)									
Other, of those with information (%)									
Missing, of total (%)									

COPD=Chronic obstructive pulmonary disease; DAS: Disease activity scale; DMARD=disease modifying antirheumatic drug; HAQ= health assessment questionnaire; Hx=history IQR=interquartile range; MI=myocardial infarction; N=count; NSAID = non-steroidal anti-inflammatory drug; RA=Rheumatoid Arthritis; TNFi=tumor necrosis factor inhibitor.

090177e199570500\Approved\Approved On: 13-Feb-2022 20:25 (GMT)

Table II. Total number of events, crude and standardized incidence rates							
Outcome	Cohort	Patients	Events	Person-Years	IR	Std IR	Mean follow-up, yrs
For each event of interest							
	Tofacitinib						
	0 previous biologics						
	1 previous biologics						
	2 previous biologics						
	3+ previous biologics						
	Third bio starters, TNFi						
	Third bio starters, non-TNFi						
	Second bio starters, TNFi						
	Second bio starters, non-TNFi						
	First bio starters, TNFi						
	First bio starters, non-TNFi						
	Bonaïve RA Patients						
	General Population						
Notes: IR, Incidence Rate, RA=rheumatoid arthritis; Std IR standardised incidence rate to the age/sex distribution in the tofacitinib cohort; TNFi=tumor necrosis factor inhibitor; yrs=years.							

090177e199570500\Approved\Approved On: 13-Feb-2022 20:25 (GMT)

090177e199570500\Approved\Approved On: 13-Feb-2022 20:25 (GMT)

Table III. Results from adjusted Cox regressions comparing tofacitinib initiators to comparator cohorts for each outcome									
Outcome	Tofacitinib initiators vs.	HRa	95% CI	HRb	95% CI	HRc	95% CI	HRd	95% CI

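### Serious infection and herpes zoster are ascertained differently by RA status, so contrasts with the general population may be biased

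*Protocol*

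**What the plan says.** Appendix 4 gives serious infections a base route, "Hospitalizations in the Patient Register listing as main diagnosis ICD10-codes below", and an extension, "If main diagnosis is RA, contributory diagnoses are also considered". Herpes zoster has the same structure: "Hospitalizations in the Patient Register listing as main diagnosis ICD10-codes B00 and B02", followed by the same extension. No other main diagnosis opens the contributory positions. Elsewhere in Appendix 4, GI perforation, PML and MACE have no condition tied to RA.

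Section 9.2.1.4 defines the controls: "Randomly selected from general population and region-, age- and gender-matched to RA patient cohorts, up to 5 population controls per tofacitinib exposed patient". RA is not stated as an exclusion. Section 9.2 gives the background frequency: "The prevalence of RA in Sweden is around 0.7% and the overall incidence 41/100,000 per year".

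Section 9.1 states: "Data capture and follow-up methods are the same for all four cohorts within the Swedish Registers". Section 8 plans general-population rates unconditionally, as context for the tofacitinib rates. Subject to feasibility, event rates "will be compared between tofacitinib-treated RA patients and other comparator cohorts using multivariable Cox regressions". In Appendix 2, Table II has a general-population row with crude and standardised rates, and Table III is titled "Results from adjusted Cox regressions comparing tofacitinib initiators to comparator cohorts for each outcome", with its comparator rows left blank.

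**The concern.** A stay with RA as main diagnosis and a listed infection code in a contributory position is an event. A stay with another chronic disease as main diagnosis and the same infection code is not. The first kind of stay occurs almost only in the RA cohorts. The rule is worded once for everyone, but in practice it gives the RA cohorts a way to qualify that population controls lack.

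Serious infection is in the study title, and section 7.1 calls it an important identified risk. The population rate is there so that a reader can judge how far the tofacitinib rate lies above background. If part of that distance comes from the extension, standardising to age and sex does not remove it, because the difference lies in how the outcome is recorded. Section 9.9 mentions endpoint misclassification in general terms but not this asymmetry, and Appendix 4 says the infection algorithm has not been specifically validated in ARTIS.

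**Working it through.** The protocol states no figure on this point, so there is nothing to reproduce. The arithmetic below shows what the rule can do.

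**Inputs.** The case definition is from Appendix 4. The share of controls with RA, p, is taken as 0.7% (section 9.2), with 2% as a check because matched controls may resemble RA patients in age and sex. The share of RA-cohort events found only through the extension, q, is not in the protocol. It is assumed to lie between 2% and 30%.

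**Step 1: written rule against a main-diagnosis-only rule in all cohorts.** Per event found by main diagnosis, the extension adds q/(1-q) events in RA patients, and p times that among controls. The RA-versus-population rate ratio changes by

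[1 + q/(1-q)] / [1 + p·q/(1-q)], which is close to 1/(1-q) when p is small.

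| q (assumed) | 1/(1-q) | p = 0.7% | p = 2% |
|---|---|---|---|
| 2% | 1.02 | 1.020 | 1.020 |
| 5% | 1.05 | 1.052 | 1.052 |
| 10% | 1.11 | 1.110 | 1.109 |
| 20% | 1.25 | 1.248 | 1.244 |
| 30% | 1.43 | 1.424 | 1.416 |

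Controls who have RA themselves barely matter. On the rate scale, at the 30 per 1000 person-years that section 9.5 assumes for bDMARD patients, q = 10% means 0.10 × 30 = 3 events per 1000 person-years from the extension alone.

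**Step 2: written rule against the truth.** Let g be the share of true infection admissions in RA patients that are coded with RA as main diagnosis, where a control's would have the infection as main. Let h be the number of incidental infection codes in RA-main stays per true infection admission. Suppose main-diagnosis coding captures the controls' infection admissions correctly. Then, relative to the true ratio:

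- main-diagnosis-only rule: 1 - g
- written rule: 1 + h
- the two are linked by 1 - q = (1 - g)/(1 + h)

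The same q fits opposite situations. Take q = 10%:

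- g = 10%, h = 0: written rule 1.00, main-only rule 0.90. The extension repairs an undercount.
- g = 0, h = 0.10/0.90 = 0.111: written rule 1.11, main-only rule 1.00. The extension creates an excess.

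More widely, g from 5% to 20% with h = 0 puts the main-only rule at 0.95 to 0.80, with the written rule at 1.00. With g = 0 and h from 5% to 20%, the written rule is at 1.05 to 1.20. The protocol gives neither g nor h.

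**Step 3: comparisons among RA cohorts.** Tofacitinib, bDMARD and ts/bDMARD-naïve patients can all use the extension, so no factor follows from the rule itself.

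**The case against.** The strongest reply is that the extension may be there to make the cohorts comparable. If infection admissions in RA patients are often coded with RA first, a main-diagnosis rule would undercount them and could hide a safety signal. Step 2 shows that this is possible, and the documents cannot exclude it. It rules out replacing the written definition with main-diagnosis-only. A reader might infer that the RA rates are inflated by the definition. The documents support that only relative to a main-diagnosis rule, not relative to the truth.

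A reader might also infer bias in tofacitinib versus bDMARD, through channelling of severe disease and more frequent RA admissions. That needs q to differ between RA cohorts, for which the documents give no figure. The Table III models also adjust in part for prior inpatient days, infection history and, in the fuller models, disease activity. That inference is not supported here.

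The stakes are also limited. Hazard ratios depend on feasibility, section 9.7.2 names only tofacitinib versus bDMARDs as a formal comparison, and the fuller Table III models use RA measures that controls lack. This stands for the hazard ratios, but the Table II population rates are planned in any case.

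Section 9.7.2 leaves a final algorithm to the SAP, and Appendix 2 says outcome details are agreed before each report. However, the promised alignment is with other registers, not between this study's cohorts, and Appendix 4 already states a rule.

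Finally, section 9.1 can be read as describing data sources and a single rule applied to all. On that reading it is not contradicted. It still invites the reader to assume equal ascertainment, so it needs a qualifier.

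**Conclusion.** The point holds as a difference in ascertainment by RA status, for serious infection and herpes zoster, in contrasts with the general population. Against a common main-diagnosis rule, the RA-versus-population ratio is higher by about 1/(1-q): 1.05 to 1.25 for q of 5% to 20%. Every value of q is an assumption. Whether the written rule overstates the true ratio, or a main-diagnosis rule would understate it, depends on coding practice that the protocol does not describe. Bias is therefore possible, and its size is unknown. The finding does not extend to comparisons among RA cohorts.

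**What to change.** Keep the written definition and make these changes:

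1. In Appendix 4 and Table II, add a sensitivity analysis for both endpoints that applies one identical rule to every cohort: once with main diagnosis only, and once with a listed code in any position. Do the same in Table III if hazard ratios against the general population are run.
2. Report, per cohort, the number of events that qualify solely through the RA-main extension. This replaces the assumed q with an observed one.
3. Name the asymmetry in section 9.9, and qualify the section 9.1 statement so that it does not imply equal outcome ascertainment by RA status.

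The cost is one extra outcome flag on Patient Register data that the study already links, a few more table rows and two sentences of text. Neither identical rule should be presented as the true one. If the results agree, the population contrast is robust to the rule; if they differ, the reader sees by how much.
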